### **Missing joint assessments**

Several deviations have occurred indicating missing joint assessments and in the main model these were assumed as 0. Since these will impact directly on the primary outcome (see section 7.1), a sensitivity analysis will be conducted on the main primary model replacing these assessments as missing. This will result in missing DAS-28 scores and as per section 11.2.3, they will be imputed as treatment non-responders.

#### **11.5.1.2 Supplementary analyses**

##### **Repeated measures logistic regression**

To account for longitudinal data, a repeated measures logistic regression analysis maybe carried out if sample size and the number of treatment responders allows for convergence. The model in section 11.5.1 will be used with the addition of week and week-by-trial arm interaction as fixed effects and participant as a random effect. All available data will be used in the analysis with  $DAS28ESR \leq 2.6$  at a visit considered as response at that visit. Missing outcome data will be imputed as treatment non-responders. If there are convergence issues then using the QR decomposition of the variance-components matrix will be considered.

The conditional odds ratio (conditional on the covariates and assuming have the same random effect) for each visit along with 95% CIs will be reported. The marginal proportions and difference in marginal proportions will be calculated from the model coefficients. Two-sided bias-corrected 95% CIs will be calculated via non-parametric bootstrapping.

##### **Change from baseline to Week 24 in DAS28ESR score**

An additional analysis will be carried out using the DAS28ESR as a continuous measure instead of converting to a binary response, since information is lost when a variable is dichotomised.

The continuous DAS28ESR score will be summarised by visit, overall and by treatment arm.

The continuous DAS28ESR score will be analysed using a repeated measures mixed-effects linear regression model, with the change from baseline in DAS28ESR score at Weeks 4, 12 and 24 as the dependent variable, adjusting for baseline DAS28ESR, trial arm, age (at baseline), gender, smoking status (binary; current or previous vs never), week and trial arm-by-week interaction as fixed effects and including the participant as a random effect. An unstructured covariance matrix will be used to describe the correlations between DAS28ESR and visits for a participant. If this model fails to converge then other covariance matrix structures will be considered. The denominator degrees of freedom will be calculated using the Kenward-Roger method. All available data will be used in the analysis and no imputation will be made for missing data. If the model assumptions are not met, then transformations of variables or alternative regression models may be used.

The marginal mean estimate, mean difference between trial arms and associated Wald 95% CIs and p-values will be reported for each time point.

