### 12.4 Change from baseline in DAS28ESR score

The change from baseline in DAS28ESR score will be considered in arms A vs B at 12 weeks and in arms B vs C at 12 and 24 weeks. The model specified in the latter section of 11.5.1.2 will be repeated but considering the relevant combinations of timepoint and trial arm comparisons.

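### The supplementary continuous DAS28ESR model fits one baseline slope to all three visits, so its Week 24 A-vs-B difference is only partly adjusted if the arms differ at baseline and that slope varies by visit

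*SAP*

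**What the plan says.** Among the supplementary analyses in SAP 11.5.1.2 is a repeated-measures linear model "with the change from baseline in DAS28ESR score at Weeks 4, 12 and 24 as the dependent variable". Its covariates are listed as "adjusting for baseline DAS28ESR, trial arm, age (at baseline), gender, smoking status", followed by "week and trial arm-by-week interaction as fixed effects and including the participant as a random effect". The only interaction named is arm by week.

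On the covariance, the SAP states: "An unstructured covariance matrix will be used to describe the correlations between DAS28ESR and visits for a participant". On reporting: "The marginal mean estimate, mean difference between trial arms and associated Wald 95% CIs and p-values will be reported for each time point". The Week 24 contrast between Arms A and B is therefore reported with its own interval and p-value. If the model fits poorly, the provision is: "If the model assumptions are not met, then transformations of variables or alternative regression models may be used".

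SAP 12.4 takes the same model over: "The model specified in the latter section of 11.5.1.2 will be repeated but considering the relevant combinations of timepoint and trial arm comparisons". The contrasts covered there are Arm A against Arm B at Week 12, and Arm B against Arm C at Weeks 12 and 24.

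Under SAP section 9 and Protocol 12.9, patients with a normal naïve CD4+ T-cell frequency go to Arm A. Only those with an abnormal frequency are randomised, to B or C.

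**The concern.** When the outcome is change from baseline, its slope on baseline becomes steeper as the correlation between baseline and follow-up falls. Some fall between Week 4 and Week 24 is plausible here. Corticosteroids may be given at baseline and at later visits (Protocol 9.3, 9.4), and DMARD treatment is escalated under treat-to-target, with the remission target assessed at Week 12 (Protocol 7.7, 9.4.2).

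A model with one slope then fits a weighted average of the three visit-specific slopes. The unstructured covariance does not free the slope; it only sets the weights. If the correlation is highest at Week 4 and the follow-up SD is stable, Week 4 has the smallest residual variance and dominates, so the common slope is too shallow for Week 24.

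In a randomised comparison this mainly costs precision. A vs B is not randomised, so baseline adjustment also has to deal with confounding by initial disease activity. What is left unadjusted passes into the arm difference, in favour of the arm with the higher baseline score, whose larger expected fall is credited to the arm.

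**Working it through.** **The plan's own figures.** The documents give no expected difference, SD or correlation for this model, so there is no figure of theirs to reproduce. The stated sample size belongs to the primary endpoint and is not in dispute. The pooled two-proportion formula (25% vs 68%, 2.75:1, two-sided 5%, 80% power) gives 13.32 in Arm B and 13.32 × 3.75 = 49.94 in total; × 1.05 = 52.43, which rounds up to the stated 53.

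**Assumptions.** Baseline SD 1.2; follow-up SD 1.3 at every visit; complete data; age, gender and smoking ignored; no true arm effect. Correlations among the follow-up visits are 0.65 (Weeks 4–12), 0.50 (4–24) and 0.65 (12–24). Arm sizes are the plan's 44/16 and 46/30.

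**Formulas.**
- Slope of change on baseline at visit t: b_t = ρ_t × 1.3/1.2 − 1, where ρ_t is the correlation of the visit-t score with baseline.
- Common slope: Σ w_t b_t, with w proportional to S⁻¹ times a vector of ones. S is the residual covariance of the three visits given baseline.
- Week 24 bias in A minus B: (b_24 − common slope) × (baseline mean A − baseline mean B).

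**Results at a baseline gap of 0.6 units.**

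| ρ at Weeks 4/12/24 | Slopes b_t | Weights | Common slope | b_24 − common | Week 24 bias |
|---|---|---|---|---|---|
| 0.4/0.4/0.4 | −0.57/−0.57/−0.57 | 0.39/0.22/0.39 | −0.57 | 0 | 0 |
| 0.6/0.5/0.4 | −0.35/−0.46/−0.57 | 0.49/0.22/0.29 | −0.436 | −0.131 | −0.08 |
| 0.7/0.5/0.3 | −0.24/−0.46/−0.68 | 0.63/0.22/0.15 | −0.355 | −0.320 | −0.19 |

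With follow-up correlations of 0.60/0.40/0.65 instead, the last row has a common slope of −0.371 and a bias of −0.304 × 0.6 = −0.18. The share of the baseline effect left unadjusted at Week 24 is 0.131/0.567 = 23% in the second row and 0.320/0.675 = 47% in the third.

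**Against the standard error.** Ignoring the small contribution from estimating the slope, SE ≈ 1.3 × √(1 − ρ_24²) × √(1/n_A + 1/n_B). For 44/16 this is 1.24 × 0.292 = 0.36 at ρ_24 = 0.3 and 1.19 × 0.292 = 0.35 at ρ_24 = 0.4. For 46/30 it is 0.29 and 0.28.

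**Simulation.** With 2,000 trials per setting, a gap of 0.6 and correlations 0.7/0.5/0.3, the mean Week 24 bias was about 0.19 in size. Coverage of the 95% interval was 92% (44/16) and 91% (46/30). With a baseline-by-week term, bias was about 0 and coverage 94 to 96%. A separate simulation (3,000 runs, 44/16, gap 0.5) gave:
- equal slopes: bias 0.005, coverage 0.951;
- correlations 0.55/0.45/0.35: bias −0.052, coverage 0.951;
- correlations 0.65/0.45/0.25: bias −0.157, coverage 0.934. With the interaction these became −0.005 and 0.952.

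**Is a gap of 0.6 reasonable?** The sample-size section uses a variance inflation factor of 1.05 from pilot data. If that reflects the association of arm with baseline DAS28, the only covariate in the protocol's primary model, then d² × p(1 − p) = 0.05, with d the gap in SDs and p the share in Arm A. For 44/16, d = √(0.05/0.196) = 0.51 SD, or 0.61 units at SD 1.2. For 46/30, d = √(0.05/0.239) = 0.46 SD, or 0.55 units. The SAP does not say what the factor refers to, so this is only a rough guide.

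**Week 12, for SAP 12.4.** The Week 12 slope (−0.458) lies close to the common slope. At a gap of 0.6 the bias is (−0.458 + 0.436) × 0.6 = −0.01 in the milder case and (−0.458 + 0.355) × 0.6 = −0.06 in the stronger one.

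**The case against.** The strongest reply is that two conditions must hold together and the documents establish neither. A reader might infer that a baseline difference alone leaves Week 24 under-adjusted. It does not: with equal slopes the bias is exactly zero whatever the gap. This stands, and so the point is conditional.

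A reader might also infer that this model is the main support for the trial's primary claim, since the SAP adds it because dichotomising loses information. The SAP does not give it that role. It is listed as supplementary, and the hypothesis in SAP 11.2.1 concerns remission proportions. That hypothesis is tested by the logistic model at Week 24 in SAP 11.5.1, which adjusts for baseline at that single visit and has no such constraint.

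Larger gaps give worse figures, but nothing in the documents points to them. A gap of 1.0 unit would imply a variance inflation factor of about 1.14 to 1.17 on the reading above, not 1.05.

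It is tempting to extend the point to the repeated-measures logistic model, which is built in the same way, "with the addition of week and week-by-trial arm interaction as fixed effects and participant as a random effect". That is not supported. Its outcome is remission at a visit, so the change-score argument does not carry over directly, and nothing was calculated for it. It is also optional and depends on convergence. With 16 × 0.25 = 4 expected responders in Arm B at Week 24, extra interactions could make convergence harder.

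Finally, the SAP permits alternative models if assumptions fail, and a common slope is such an assumption. This is a partial answer: no check of the slope is named, and a term added after seeing the results would be post hoc.

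**Conclusion.** The point holds as a conditional risk in one supplementary analysis. The model imposes a common baseline slope, A vs B is not randomised, and the SAP has no specific safeguard. If the arms differ at baseline and the slope varies by visit, the Week 24 mean difference is only partly adjusted.

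At an assumed gap of 0.6 units the bias ranges from 0 to about 0.19 DAS28 units. That is at most about half the standard error at 44/16 (0.19/0.36) and about two-thirds at 46/30 (0.19/0.29). The cost is a few points of coverage, not a reversal of conclusions. These figures rest on the assumed SDs, correlations and gap, none of which the documents state. In SAP 12.4 little bias is at stake: 0.01 to 0.06 units for A vs B at Week 12, and only chance imbalance and precision for the randomised B vs C comparison.

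**What to change.** In SAP 11.5.1.2, add a baseline DAS28ESR-by-week interaction to the fixed effects of the continuous change-from-baseline model. Let SAP 12.4 inherit it so that the two sections use the same model. No change is needed to the primary analysis, the sample size or the repeated-measures logistic model.

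The cost is one phrase and two extra parameters in 60 or more patients with up to three visits each. In the simulations with no baseline gap, the Week 24 standard error was unchanged to 4% smaller; the worst case, a milder fall in correlation with a large gap, was about 3% larger. With equal slopes, a gap of 0.5 and 44/16 patients, the SD of the estimate was 0.354 with the term and 0.352 without.

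The change should be made before the statistician receives the arm codes (Protocol 12.10). If that has already happened, report the model with the interaction as an additional sensitivity analysis, labelled as post hoc.

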#### **11.5.1.3 Subgroup analyses**

There are no planned subgroup analyses.

### **11.6 Analysis of secondary outcomes**

The secondary outcomes will each be summarised descriptively by trial arm and overall at each time point, including the level of missing data.

### **11.6.1 Proportion of participants achieving clinical remission at Week 12 between Arms A and B**

This outcome will be analysed and reported as outlined for the primary outcome in Section 11.5.1, with the outcome switched to the proportion of participants achieving clinical remission (DAS28ESR $\leq$  2.6) at Week 12 in Arms A and B as opposed to Week 24.

### **11.6.2 Proportion of participants achieving clinical remission at Weeks 12 and 24 between Arms B and C**

The difference in proportion achieving clinical remission at Weeks 12 and 24 in Arm B vs Arm C will be analysed as described in section 11.5.1. The proportions, unadjusted and adjusted odds ratios with a range of CIs (75%, 85%, 90% and 95%) will be presented.

### **11.6.3 Differences in the medians of PROMs at Weeks 12 and 24 between Arms A and B**

Patient-reported outcomes (EMS, each VAS, HAQ-DI) at Weeks 12 and 24 will be summarised descriptively between arms A and B, means and standard deviations or medians and interquartile range (if skewed) will be presented.

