12.5.2. Secondary endpoint analyses

Secondary endpoint analyses will be conducted in the FAS. The proportions of patients in clinical and imaging remission at 3 & 6 months will be compared between arms A and B in the same manner as the primary analysis (analyses of imaging remission will adjust for the number of joints scoring PD>0 at baseline).

Patient-reported outcomes at 3 and 6 months will be compared between arms A and B using non-parametric quantile (median) regression, controlling for baseline values in each case. Unadjusted and adjusted differences will be presented, together with 95% confidence intervals.

For comparisons between Arms B and C, descriptive summaries of all endpoints will be presented within each arm. Unadjusted and adjusted between-group differences and a range of 90% confidence intervals (75%, 85%, 90%, 95%) will be presented but no inferential tests will be conducted. Assuming preliminary proof of concept is obtained (i.e. the proportion of patients in clinical remission at 6 months is higher in arm C than arm B), sample size

calculations will be performed for a range of plausible and clinically meaningful between-group differences

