## 5.2 Secondary objectives

- To determine the proportion of patients that achieve clinical remission for patients with abnormal baseline naïve CD4+ T-cell frequencies receiving etanercept + MTX (Arm C) to obtain preliminary proof-of-concept of superior response compared to MTX with T2T care (Arm B).
- To determine whether the proportion of patients that achieve imaging remission after first-line treatment with MTX differs according to naïve CD4+ T-cell frequency (normal/abnormal) at baseline (Arm A vs. Arm B).
- To determine the values of patient-reported outcomes (EMS, VAS scales, HAQ-DI) for patients with abnormal baseline naïve CD4+ T-cell frequencies receiving etanercept + MTX (Arm C) to obtain preliminary proof-of-concept of superior response compared to MTX with T2T care (Arm B).
- To determine whether patient-reported outcomes (EMS, VAS scales, HAQ-DI) after first-line treatment with MTX differ according to naïve CD4+ T-cell frequency (normal/abnormal) at baseline (Arm A vs. Arm B).
- To determine the proportion of patients that achieve imaging remission for patients with abnormal baseline naïve CD4+ T-cell frequencies receiving etanercept + MTX (Arm C) to obtain preliminary proof-of-concept of superior response compared to MTX with T2T care (Arm B).
- To determine the proportion of patients who normalize their T-cell status for patients with abnormal baseline naïve CD4+ T-cells receiving MTX with T2T care or etanercept + MTX (Arm B & Arm C).
- To determine whether the proportion of patients achieving sustained clinical remission differs between study arms.
- To determine whether the cumulative amount of corticosteroid use differs between study arms.

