### 11.2 Analysis principles and populations

For all analyses, unless otherwise stated, the analysis set will include all randomised participants. Analysis sets are given in Table 2.

*Table 2: Analysis data sets*

Analysis set	Description
Full analysis set (FAS)	The FAS will include all patients randomised and not withdrawn from the study prior to or during their baseline visit. Following the intent-to-treat principle, patients will be analysed according to the treatment assigned irrespective of treatment received.
Per protocol set (PPS)	The PPS will include patients in the FAS who have no significant deviations from the protocol that may influence the viability of the data.

Safety set	The Safety set will include all patients who took at least 1 dose of study treatment during the treatment period. Patients will be evaluated according to study treatment received.
------------	---

The full analysis set will be used for all efficacy analyses unless specified otherwise and the safety set for safety analyses. Statistical tests for the primary and secondary outcomes comparing Arm A vs Arm B will be two-sided at the 5% significance level and 95% confidence intervals (CIs) shall be used. For the secondary outcomes comparing Arm B vs Arm C, no inferential tests will be carried out.

Due to the lower limit of reliable CRP detection being 5; values less than 5 will be recorded as 0 in the data. It will be assumed these values were uniformly distributed between 0 and 5 and hence will be replaced as 2.5 in the calculation of any scores (for example in calculating SDAI).

In general, summary statistics [n (number of available measurements), arithmetic mean, standard deviation, median, minimum, and maximum] for quantitative variables and absolute and relative frequency tables for qualitative data will be presented.

A table template to illustrate this with the primary outcome measure is given in appendix 1.

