### **11.6.5 Differences in the proportion of participants achieving imaging remission at Week 24 between Arms A and B**

The proportions of patients in imaging remission (PD=0) at Week 24 will be summarised descriptively by arm and overall for Arms A and B.

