### 13.1 Changes to protocol planned analysis

The following changes were made to the protocol planned analysis due to the statistician at Leeds leaving and the analysis being taken over by the YTU:

- Protocol section 12.5.2: Secondary analyses of imaging and PROMs outcomes removed, only descriptive statistics will be produced
- Protocol section 12.5.3 and 12.7: Sensitivity analyses updated to only be carried out for the primary outcome
- Protocol section 12.5.3: Supplementary analyses added to include a repeated measures logistic regression model and considering the change in continuous DAS28 score from baseline via a repeated measures linear regression model.
- Protocol section 12.4 Full analysis set to include all randomised patients who were not withdrawn from the study prior to or during their baseline visit rather than just randomised.

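### SAP 11.6.3 and 11.6.5 specify only arm-level summaries for A vs B patient-reported outcomes and imaging remission, contradicting SAP 5.2, 7.2.2, 7.2.3 and 11.2 and dropping the protocol's baseline-adjusted estimates

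*SAP*

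**What the plan says.** **Objectives.** SAP 5.2 sets two comparative secondary objectives for A vs B, each by baseline naïve CD4+ T-cell status. One begins "To determine whether patient-reported outcomes (EMS, VAS scales, HAQ-DI) after first-line treatment with MTX differ according to" that status. The other begins "To determine whether the proportion of patients that achieve imaging remission after first-line treatment with MTX differs according to" it. Protocol 2.4 carries the same two.

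**Outcome definitions.** SAP 7.2.2 says the differences in medians at Weeks 12 and 24 will be calculated for A vs B. SAP 7.2.3 says the same of the difference in imaging-remission proportions at Week 24.

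**General rule.** SAP 11.2: "Statistical tests for the primary and secondary outcomes comparing Arm A vs Arm B will be two-sided at the 5% significance level". It adds that 95% confidence intervals will be used.

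**Analysis sections.** SAP 11.6.3: "Patient-reported outcomes (EMS, each VAS, HAQ-DI) at Weeks 12 and 24 will be summarised descriptively between arms A and B". It goes on to offer means with SDs, or medians with interquartile ranges where the data are skewed. SAP 11.6.5: "The proportions of patients in imaging remission (PD=0) at Week 24 will be summarised descriptively by arm and overall for Arms A and B". Both section titles still speak of differences.

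**Protocol.** Protocol 12.5.2 says patient-reported outcomes "will be compared between arms A and B using non-parametric quantile (median) regression, controlling for baseline values in each case", with unadjusted and adjusted differences and 95% intervals. Imaging remission was to be analysed as the primary endpoint is, by logistic regression, adjusting for the baseline count of joints with a power Doppler score above 0.

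**Logged change.** SAP 13.1: "Secondary analyses of imaging and PROMs outcomes removed, only descriptive statistics will be produced". The reason given for all the listed changes is that the statistician left and another trials unit took over the analysis.

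**The concern.** A secondary objective that asks whether two groups differ needs an estimate of the difference and a statement of its uncertainty. The sections that tell the analyst what to do specify neither, while other sections of the same SAP promise both. Two competent analysts could follow this SAP and deliver different reports. Section 11.6.3 does not even guarantee medians, since it allows means when the data are not skewed, although the endpoint is a difference in medians.

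Adjustment matters here because arms A and B are formed by T-cell status, not by randomisation. The SAP accepts this for the primary endpoint, where 11.5.1 adjusts for baseline DAS28ESR, age, gender and smoking. For these two sets of outcomes the baseline values are collected (Protocol 9.1), but no adjusted comparison is specified.

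**Working it through.** **1. The sections side by side**

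| SAP section | What it implies for A vs B on these outcomes |
|---|---|
| 5.2 | Establish whether they differ |
| 7.2.2, 7.2.3 | Calculate the differences |
| 11.2 | Two-sided 5% tests, 95% intervals |
| 11.6.3, 11.6.5 | Summaries by arm; no model, estimate, interval or test |
| 13.1 | Protocol analyses removed; description only |

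The first three rows cannot be reconciled with the last two. By contrast, SAP 11.6.9 does specify an unadjusted between-arm difference for corticosteroid use, and 11.6.1 and 11.6.8 keep the full primary model for Week 12 and sustained clinical remission.

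**2. The plan's own sample size**

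SAP 9 and Protocol 12.9 give 68% vs 25%, A:B = 2.75:1, two-sided 5%, 80% power and variance inflation 1.05, for a total of 53. With k = 2.75 and p̄ = (0.25 + 2.75 × 0.68)/3.75 = 0.565, the pooled two-proportion formula is:

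n_B = [1.96 √(p̄(1−p̄)(1+1/k)) + 0.842 √(0.25×0.75 + 0.68×0.32/k)]² / 0.43² = 13.32

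Total = 3.75 × 13.32 = 49.94; × 1.05 = 52.4, rounded up to 53. The plan's figure is reproduced. The inflated total of 60 splits 44:16 at 2.75:1. This calculation covers Week 24 clinical remission only; the documents give no power or precision for imaging remission or patient-reported outcomes.

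**3. Precision of the imaging comparison if restored**

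Unadjusted 95% half-width = 1.96 √(p_A(1−p_A)/n_A + p_B(1−p_B)/n_B). Arm sizes are from SAP 9: 44/16 and 46/30 are the stated extremes, and 46/17 follows from at least 46 in A and at least 34 randomised 1:1. The documents give no imaging-remission rates, so the rates below are assumptions; 68%/25% borrows the clinical-remission targets.

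| A/B | 50%/50% | 68%/25% | 80%/60% |
|---|---|---|---|
| 44/16 | 28.6 | 25.3 | 26.8 |
| 46/17 | 27.8 | 24.6 | 26.0 |
| 46/30 | 23.0 | 20.5 | 21.0 |

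(percentage points). Example: 1.96 √(0.25/46 + 0.25/17) = 0.278. With the 50% variance, an observed gap of 20 points would carry an interval of about −8 to +48 at 46/17, or −3 to +43 at 46/30.

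**4. Precision of a median difference**

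Assuming normal data, half-width = 1.96 × 1.2533 × SD × √(1/n_A + 1/n_B). This is 0.72 SD at 44/16 and 0.58 SD at 46/30. No SDs are given.

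**5. Multiplicity if tests were restored**

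SAP 7.2.2 lists early morning stiffness, four visual analogue scales and HAQ-DI: 6 measures × 2 visits = 12, plus imaging = 13 comparisons. If independent and each tested at 5%, the chance of at least one false positive is 1 − 0.95¹³ = 0.49. The outcomes are correlated, so this is a guide only.

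**The case against.** The strongest defence is that the change is deliberate and disclosed, and that description suits a small study. Section 13.1 lists the removal against Protocol 12.5.2, and SAP section 1 says the plan was drafted before database lock was complete. The study was sized for clinical remission only. At 44/16, 80% power for imaging remission needs a difference of 36 to 40 points (assumed arm B rates of 30 to 50%), and 13 tests at 5% would invite false positives. This stands as an argument against tests. It does not argue against estimates with intervals, since low precision is a reason to show it. Nor does the SAP make this case: its only stated reason is staffing, while the same SAP adds repeated-measures models the protocol did not have.

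Three stronger readings are tempting, and the documents do not support them.

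- A reader might infer that the SAP as a whole provides no difference, interval or test. Sections 7.2.2, 7.2.3 and 11.2 promise them, so the defect is a contradiction and not a proven absence.
- A reader might infer that baseline imbalance is ignored. Section 11.6 summarises each outcome by arm and time point, and SAP Appendix 1 says tables like its shell, which has baseline columns, will follow for these outcomes. Imbalance would be visible but not adjusted for.
- A reader might infer that all information on uncertainty is lost. Reported imaging counts let anyone compute an unadjusted interval. What cannot be recovered from arm summaries is the adjusted estimate, or an adjusted median difference and its interval.

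**Conclusion.** The point holds as an internal contradiction together with the loss of planned baseline-adjusted estimates in a non-randomised comparison. It affects two secondary objectives. The primary, Week 12 and sustained clinical-remission analyses are untouched, so this should be corrected but does not threaten the main result.

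Restored intervals would be wide: about 21 to 29 points for imaging remission and 0.58 to 0.72 SD for a median difference. These figures rest on assumed remission rates, on normal data for the medians, on the planned arm sizes with no loss to follow-up, and on unadjusted formulas. The contradiction itself rests on the text alone and depends on none of these assumptions.

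**What to change.** - **SAP 11.6.3:** for each patient-reported outcome at Weeks 12 and 24, report unadjusted and baseline-adjusted A vs B median differences with 95% intervals from median regression.
- **SAP 11.6.5:** analyse Week 24 imaging remission by logistic regression adjusted for the baseline number of joints with power Doppler above 0. Report odds ratios and the marginal difference in proportions with 95% intervals, using the method of 11.5.1. The marginal step is needed because the protocol's model yields odds ratios, whereas the endpoint is a difference in proportions. Restrict this to Week 24: Protocol 12.5.2 also mentions 3 months, but ultrasound is scheduled only at baseline and Week 24, apart from flare visits.
- **SAP 11.2:** label these estimates as secondary and not controlled for multiplicity, and reword the general rule so that it does not attach uncontrolled 5% tests to them.
- **SAP 13.1:** revise the bullet that removes these analyses.

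The cost is a little programming on data already collected, some rewording, and wide intervals in the report. If the sponsor keeps description only, the minimum is a scientific reason in 13.1 and matching descriptive wording in 5.2, 7.2.2, 7.2.3 and 11.2. That removes the contradiction but leaves the two objectives, as now stated, unanswered.
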